9.10. Early Discontinuation/Withdrawal of Participants

During the course of the study, a participant may choose to withdraw from future study procedures. Participants may also withdraw their consent, meaning that they wish to withdraw from the study completely. They may also withdraw consent for continued storage of their blood samples. Alternatively, they may lose the capacity to consent during the study or even die (since there is no age limit on participation). Finally, participants may withdraw from the study simply because they leave the household which was originally sampled – it is the physical household location that is sampled so if they move, their participation finishes. The study team may also withdraw a household for unreasonable behaviour in exceptional circumstances, for example, repeatedly touching study workers at non-contact visits despite being requested to maintain social distancing or being verbally abusive.

Each participant has the right to withdraw from the study at any time; individual participant withdrawal will not mean others in the household are automatically withdrawn, each participant will make their own individual decision.

De-identified data obtained up to the point of consent withdrawal will be kept and used in analysis for all participants who withdraw, regardless of type of withdrawal (described below) and this is explained in the Participant Information Sheet.

Participants who wish not to continue participation in some or all parts of the study will therefore have the following options, and the type of withdrawal recorded.

- Participants may withdraw from active follow-up (i.e. future study procedures) and further communication but allow the study team to retain their personal identifiable information in order to continue to access their ONS and NHS records for future electronic follow-up. Residual serum samples would be kept for future research.
- 2) Participants can withdraw from active follow-up (i.e. future study procedures) and further communication and also request their personal identifiable information be removed so that their study records cannot be linked to ONS and NHS records for future electronic follow-up. De-identified data and samples obtained up until the point of withdrawal would be retained for use in the study analysis, and any residual serum samples to be used for future research. No further data or samples would be collected after withdrawal.
- 3) Participants can withdraw completely from the study and withdraw their samples collected up until the point of withdrawal. The data already collected would be used in the analysis, but samples would be destroyed if not already analysed and any residual serum samples already

Clinical Research Protocol Template version 15.0

being stored would also be destroyed. Personal identifiable information would be removed so that their study records cannot be linked to ONS and NHS records for future electronic follow-up.

Participants who lose capacity to consent during the study will be withdrawn from active follow-up (option 1). Participants who withdraw for any reason will not be specifically replaced; rather ongoing recruitment will be to maintain the overall swab and blood targets described above, accounting for both withdrawals and intermittent missed visits without withdrawal. If a participant dies, immediate visits will be cancelled, and the household will be written to, asking them to call the contact centre if they would like to restart visits, but that otherwise we will not make further contact. This provides family members with the freedom to make their own personal decision about further participation.

9.11. Definition of End of Study

The end of the study is the date of the last assessment of the last participant.

10. SAFETY REPORTING

There are no interventions in this study, and the only procedures are a participant fingerprick blood draw using methods which have been widely used in other serology studies and for commercial antibody testing, and a participant self-swab (or parent/carer swab of a child) using a methodology which is being used widely at drive through testing centres across the country. Therefore, there is minimal safety risk to participants.

However, any serious adverse event **which is considered related to any of the study procedures** will be reported to the Sponsor. A serious adverse event is defined as any untoward medical occurrence that

- Results in death
- Is life-threatening (with a real, not hypothetical, risk of death at the time)
- Requires inpatient hospitalization or causes prolongation of existing hospitalization
- Results in persistent or significant disability/incapacity
- Has a real, not hypothetical, risk of one of the above

Other 'important medical events' may also be considered a serious adverse event when, based upon appropriate medical judgement, the event may jeopardise the participant and may require medical or surgical intervention to prevent one of the outcomes listed above.

NOTE: The term "life-threatening" in the definition of "serious" refers to an event in which the participant was at risk of death at the time of the event; it does not refer to an event which hypothetically might have caused death if it were more severe.

10.1. Reporting Procedures for Serious Adverse Events

A serious adverse event (SAE) occurring to a participant should be reported to the REC that gave a favourable opinion of the study where in the opinion of the Chief Investigator the event was 'related' (resulted from administration of any of the research procedures) and 'unexpected' in relation to those procedures. Reports of related and unexpected SAEs should be submitted within 15 working days of the Chief Investigator becoming aware of the event, using the Health Research Authority (HRA) report of serious adverse event form (see HRA website).

11. STATISTICS AND ANALYSIS

11.1. Statistical Analysis Plan (SAP)

The statistical aspects of the study are summarised here. There is no formal Statistical Analysis Plan.

11.2. Description of the Statistical Methods

For the primary outcome, Bayesian dynamic spatiotemporal multi-level regression with poststratification (MRP) will be used to investigate changes in positivity rates over calendar time.^{25,26} Potential spatial correlation between neighbouring areas is taken into account using a "BYM2" specification. Time will be allowed to vary in a non-linear fashion by using a first-order autoregressive term for time. Space-time, and space-age interactions will be included to allow the positivity over time to vary by age and age group. This spatiotemporal MRP is an extension of the spatial MRP method developed by Gao et al.²⁷ In extensive simulations, Gao et al found that bias was significantly reduced when using a BYM2 specification compared to a non-spatial independent identically distributed specification. Attenuation in absolute bias was most apparent with small sample sizes. Even when simulating outcome data as a multivariate independent normal, BYM2 spatial prior produced nearly same posterior estimates as independent identically distributed prior, indicating that the BYM2 spatial prior does not force spatial structure when it is not present.

The reason for using MRP as the primary method is because it allows probabilistic assessment of relatively rapid changes in positivity. MRP consists of two steps. First, a multilevel regression model is used to generate the outcome of interest as a function of (socio)demographic and geographic variables. Next, the resulting outcome estimates for each demographic-geographic respondent type are poststratified by the percentage of each type in the actual overall population. In several empirical and simulation studies MRP was superior at both the national and regional levels to classical survey weighted and unweighted approaches, including when using small sample sizes.^{26,28} Factors included in the main models - besides time, space, and a space-time interaction described above – will be sex, age, ethnicity and an age-time interaction. Whether additional interactions are needed will be determined based on the Watanabe-Akaike information criterion.

In addition, the proportion of individuals with symptomatic and asymptomatic infection (based on PCR of nose and throat swabs) based on the latest result in the last two weeks will be summarised approximately every calendar week from the start of the study, overall and by geographical region. Proportions will be calculated incorporating sampling weights for the original ONS and NISRA surveys, this survey and for non-response to this survey, with 95% confidence intervals estimated using the Korn-Grauberd method which allows for the low anticipated positivity rates. We will use Bayesian methods in sensitivity analyses assessing the impact of plausible ranges of test sensitivity and specificity on results, incorporating both the assay performance and the fact that participants are self-swabbing. Associations between various predictors and ever testing positive for infection vs never testing positive will be estimated using unweighted proportions and Fisher's exact tests with multivariable logistic regression models to adjust for confounding. Factors considered will include sex, ethnicity, age at last birthday (as both categorical and continuous variables) and other responses to the short questionnaire. These factors will also be considered in multi-level regression models, similar to the main model over continuous time described above.

Similar spatiotemporal MRP methods will be used to estimate proportions over time with immunity defined based on the optical density readings from the ELISA assay for IgG antibodies versus the threshold defined in comparison with pre-pandemic plasma. We will also estimate the proportions with previous infection (as defined by antibodies) but no previous symptoms.

Random effects linear regression models will also be generated for the absolute optical density readings (potentially log-transformed depending on the distribution) in relation to time since onset of first symptoms, with those not reporting symptoms treated as an additional category (random effect per household – may be omitted depending on model fit). Additional factors considered in these models will include age, sex and ethnicity.

Incidence will be calculated indirectly by deconvoluting the Bayesian dynamic multi-level regression model estimate of swab positivity and an estimate of duration of PCR positivity based on those testing positive in the study. More details are provided on

https://www.ons.gov.uk/peoplepopulationandcommunity/healthandsocialcare/conditionsanddiseases/ methodologies/covid19infectionsurveypilotmethodsandfurtherinformation#incidence.

Through linkage to NHS records (and equivalent national databases in Devolved Administrations), we also aim to determine the impact of immunity and symptomatic/asymptomatic infection status on healthcare usage, in particular inpatient admissions, A&E attendances and general practitioner consultations. This linkage would be performed both during active study participation (i.e. whilst home visits are being conducted) and after active study participation has ended (for up to fifteen years). Through linkage to records from ONS and equivalent national mortality databases in the Devolved Administrations, we aim to determine the impact of immunity and symptomatic/asymptomatic infection status on mortality and cause of death. Through linkage to records from UKHSA and equivalent national test databases in Wales, Northern Ireland and Scotland on other tests for SARS-CoV-2, we will ensure that we obtain as accurate as possible associations between infection and immunity.

More information about the methods used in analysis can be found on

https://www.ons.gov.uk/peoplepopulationandcommunity/healthandsocialcare/conditionsanddiseases/ methodologies/covid19infectionsurveypilotmethodsandfurtherinformation.

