In April 2020, we began by inviting 20,000 households to participate with an assumed 50% opt-in rate, and a target enrolment of 10,000 households (2,500 per week over around one month). Around 2,000 of these households (500 per week) were asked to give blood. After this, in Phase II we invited new groups of around 5,000 households in England, around 500 households in Wales and around 500 households in Northern Ireland approximately every week, targeting recruitment of around 2,500, 250 and 250 new households per week respectively (total 3,000 households per week; assuming 50% consent rate; numbers approached will be increased if consent rate is lower to achieve the target enrolment). A mean of 2.1 individuals were recruited per household. In order to achieve a cohort of ~150,000 individuals sampled at least once a fortnight from October 2020 onwards when the winter season of respiratory infections starts, and monitoring for a possible "second wave" of infections was critical, from the end of July 2020 we scaled this up to inviting new groups of around 18,000 households in England, around 1,800 households in Wales, up to 1,800 households in Northern Ireland and around 4,500 households in Scotland approximately every week, targeting recruitment of around 9,000, 900, up to 900, and 2,250 new households per week respectively (total around 13,000 households per week; assuming 50% consent rate; numbers approached to be increased if consent rate is lower to achieve the target enrolment). Ultimately the swab target from October 2020 to March 2022 inclusive was to achieve ~150,000 individuals with swab test results at least every fortnight in England, ~9,000 in Wales, ~5,000 in Northern Ireland and ~15,000 in Scotland (~179,000 total across the UK) (absolute numbers reflecting the relative size of the underlying populations). To January 2021, we approached 10-20% of invited households to also give a sample of blood from enrolment. This is to find out how the number of people infected at any one time, the levels of immunity to COVID-19, and the rates of infection with and without symptoms, are changing across the country. From February 2021, we asked a representative sample of those already recruited to the study but only giving swabs to also give blood at their monthly visits, and for everyone giving blood samples to stay in the study until April 2022. The blood target from April 2021 to March 2022 inclusive was to achieve up to ~125,500 adults 16 years and older with blood test results every month in England, and up to ~7,500, ~4,500 and ~12,500 per month in Wales, Northern Ireland and Scotland (~150,000 in total across the UK) (absolute numbers reflecting the relative size of the underlying populations). This is to monitor how vaccination affects immunity at both the population and the individual level. For those aged 8-15 years, the target from December 2021 to

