11.3. Sample Size Determination

The target sample size for Phase I (around 10,000 households enrolled over one month, and around 21,000 individuals) was determined based on a conservative assumption that all members of the same household have the same infection status, and therefore each household should only be counted as one unit in the sample size calculation. If infection status varies within households, this will increase precision around our estimates.

The precision (margin of error) that various sample sizes provide around various estimates of infection rates (and seroprevalence) is illustrated in **Figure 5** below, together with the precision for smaller sample sizes, which should be achieved for specific regions and/or groups defined by other characteristics such as age. For a given prevalence p and sample size N, the expected margin of error corresponds to the expected width of the 95% confidence interval associated with the point estimate of p obtained using an exact binomial test. On balance, around 10,000 households in Phase I (around 21,000 individuals), and around 12,000 households (25,000 individuals) each subsequent month (3,000 per week) in Phase II, was

Clinical Research Protocol Template version 15.0

© Copyright: The University of Oxford and Oxford University Hospitals NHS Foundation Trust 2019 Page 67 of 113 considered to provide sufficient precision across England overall, particularly at lower prevalence rates which may be expected at earlier cross-sectional surveys, as well as the possibility of assessing evidence for variation within smaller but very important subgroups, including regions and Devolved Administrations (each targeting ~1,000 households per month, ~2,100 individuals per month).

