11.4. Analysis populations

All enrolled participants will be included in analyses, which will adjust for clustering by household wherever possible. Secondary analysis will also be conducted de-duplicating to one individual per household, for example restricting to adults targeted by ONS in the original approach letter.

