11.7. The Level of Statistical Significance

A nominal significance level of 5% will be used; however, results will be interpreted based on their 95% confidence intervals rather than using a rigid threshold approach.

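### Fisher's exact tests for ever testing positive ignore household clustering, so their error rate exceeds 5% for predictors that household members share

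*Protocol*

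**What the plan says.** Protocol section 11.2 sets out the association analysis: "Associations between various predictors and ever testing positive for infection vs never testing positive will be estimated using unweighted proportions and Fisher's exact tests". Alongside these tests it plans multivariable logistic models, whose stated purpose is to deal with confounding. On the predictors it says: "Factors considered will include sex, ethnicity, age at last birthday (as both categorical and continuous variables) and other responses to the short questionnaire". It then adds: "These factors will also be considered in multi-level regression models, similar to the main model over continuous time described above".

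Households are the sampling unit, and every consenting member aged 2 years or older is recruited. The Lay Summary reports: "A mean of 2.1 individuals were recruited per household". Table 1 gives a ratio of 2.16.

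The protocol expects dependence within households. Section 6 makes the association of infection between household members a secondary objective. Section 11.3 sizes Phase I on the conservative assumption that members share infection status, so that "each household should only be counted as one unit in the sample size calculation".

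Section 11.4 includes all enrolled participants in analyses "which will adjust for clustering by household wherever possible", and plans a secondary analysis reduced to one individual per household. Section 11.7 says: "A nominal significance level of 5% will be used; however, results will be interpreted based on their 95% confidence intervals", as opposed to a fixed cut-off. Section 11.1 states that there is no formal statistical analysis plan, so section 11.2 is the operative text.

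**The concern.** Fisher's test takes its reference distribution from reallocating individuals freely across the table. That is right only if members of the same household are independent. If both the outcome and the predictor cluster in households, the observed difference varies more under the null than the test allows, and the test rejects too often.

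The clustering rule in 11.4 does not reach this test, because the rule applies only where adjustment is possible and the standard Fisher test has no place for a household term. As written, the all-participant comparison is the one analysis that the rule cannot repair.

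At stake is the reading of factors that household members tend to share. Ethnicity is named in 11.2, and section 7 designs the expanded blood cohort for power to study it. Questionnaire items such as household contacts or isolation because of others may behave in the same way. Such factors could appear associated with infection more often than the stated 5% implies.

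**Working it through.** **Inputs.**
- Nominal level: 5% (11.7), taken as two-sided because 95% intervals are used.
- Mean household size m: 2.1 (Lay Summary) or 2.16 (Table 1).
- ICC of ever testing positive: not given, so a range from 0 to 1 is shown.
- Household-size distribution: not given. Two cases are used: all households at 2.1, and an assumed mix of sizes 1 to 5 with probabilities 0.32, 0.41, 0.14, 0.11 and 0.02.

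For the mix, the mean is 0.32 + 0.82 + 0.42 + 0.44 + 0.10 = 2.10, and the mean square is 0.32 + 1.64 + 1.26 + 1.76 + 0.50 = 5.48. The size-weighted mean is m_eff = 5.48 / 2.10 = 2.61.

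**Formulas.** For a predictor constant within households:
- design effect D = 1 + (m_eff − 1) × ICC
- actual two-sided error = 2 × [1 − Φ(1.96 / √D)]

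**The plan's own figure.** With ICC = 0, D = 1 and the error is 2 × [1 − Φ(1.96)] = 5.0%. The nominal level is reproduced only under independence.

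**Results for a household-level predictor.**

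| ICC | D, all 2.1 | Error | Ratio | D, mix | Error | Ratio |
|---|---|---|---|---|---|---|
| 0 | 1.00 | 5.0% | 1.0 | 1.00 | 5.0% | 1.0 |
| 0.1 | 1.11 | 6.3% | 1.3 | 1.16 | 6.9% | 1.4 |
| 0.2 | 1.22 | 7.6% | 1.5 | 1.32 | 8.8% | 1.8 |
| 0.3 | 1.33 | 8.9% | 1.8 | 1.48 | 10.8% | 2.2 |
| 0.5 | 1.55 | 11.5% | 2.3 | 1.80 | 14.5% | 2.9 |
| 1.0 | 2.10 | 17.6% | 3.5 | 2.61 | 22.5% | 4.5 |

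**Doubling.** An actual error of 10% needs D = (1.96 / 1.645)² = 1.42. With equal sizes that is ICC = 0.42 / 1.10 = 0.38, and with the mix it is 0.42 / 1.61 = 0.26. A slightly wider assumed mix (sizes 1 to 6, mean 2.13, m_eff 2.76) gives 0.42 / 1.76 = 0.24.

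**Fourfold.** An error of 20% needs D = (1.96 / 1.2816)² = 2.34. With all households at 2.1 the largest possible D is 2.10, so this cannot be reached. With the two mixes it needs an ICC of 0.83 and 0.76 respectively.

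**Simulation of the Fisher test itself.** The setting was 10,000 households, the sizes 1 to 5 mix, a null predictor set at household level, and 2,000 replicates. Rejection rates with 2% and 10% ever positive were:
- ICC 0: 4.4% and 5.0%
- ICC 0.2: 8.7% and 8.6%
- ICC 0.4: 13.2% and 13.4%
- ICC 0.6: 15.9% and 16.6%
- ICC 1: 21.3% and 22.5%

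These agree with the formula. A second simulation, with the predictor held by only 10% of households and a mix of mean 2.17, gave 8.5-9.3% at ICC 0.2 and about 22% at ICC 1.

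**Predictors that vary independently within households.** In 1,000 replicates per setting the rejection rate was 3.5% to 6.5%. The simulation standard error is √(0.05 × 0.95 / 1000) = 0.7 percentage points, so there is no sign of material inflation.

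**The case against.** The strongest reply is that the protocol already handles clustering. Section 11.4 applies to analyses in general, and a logistic model can plainly be adjusted for household. It would be wrong to read those models as unadjusted merely because 11.2 mentions only confounding. Section 11.4 also plans an analysis with one person per household, where Fisher's test is free of household clustering. The same factors go into multi-level models, and 11.7 rests interpretation on intervals, not on a 5% cut-off.

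Much of this stands. The logistic models fall under the 11.4 rule, and the de-duplicated analysis is a valid check. Three limits remain. The de-duplicated analysis is secondary, and its example, restriction to the adults first approached, would leave out children. The terms listed for the main multi-level model do not include household, although 11.2 does name a household random effect for the antibody readings. Interval-based reading does not make the Fisher p-values correct.

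A reader might infer a fixed inflation, such as two to four times nominal. The documents do not support that, because they give neither an ICC nor a size distribution: the factor is below two at low ICC, and four is out of reach if all households have 2.1 members. A reader might also take full concordance as the protocol's view of ever testing positive. In 11.3 it is a conservative sizing assumption about infection status, so ICC = 1 is a worst case only. Nor does the text say that Fisher's test is used to screen factors in the twice-monthly interim analyses of 11.5.

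**Conclusion.** The point holds for the all-participant Fisher tests of predictors shared within households. Followed as written, they are anti-conservative: about 6-7% at ICC 0.1, rising to about 18-22% at ICC 1, against a nominal 5%. The error is at least double once the ICC exceeds about 0.25 (unequal sizes) to 0.4 (equal sizes). These figures rest on an assumed ICC range and assumed household sizes around the protocol's mean. The upper end moves with the size mix: the wider mix above gives 23.8% at ICC 1.

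The scope is limited. These are exploratory associations. Predictors that vary independently within households, sex being the nearest example, stay near 5%, and the primary multilevel regression and post-stratification estimate does not use this test. The change is worth making because the error rate is wrong for factors of real interest and is easily corrected, but the main results do not depend on it.

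**What to change.** In section 11.2, for the all-participant analysis, replace Fisher's exact test with a household-clustered test: a Rao-Scott adjusted chi-square, or a Wald or score test from logistic regression or GEE with household-robust variance. In the same place, state that the clustering rule in 11.4 applies to the multivariable logistic models. Keep Fisher's exact test for the one-person-per-household analysis only.

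The cost is a sentence or two in 11.2 and a standard software option, since household codes are already held. The intervals become slightly wider, and exactness is lost in very sparse cells, where the one-person-per-household Fisher test remains available as a check.

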6. OBJECTIVES AND OUTCOME MEASURES

Objectives	Outcome Measures	Timepoint(s) of evaluation of this outcome measure
Primary Objective To estimate prevalence of symptomatic and asymptomatic SARS-CoV-2 infection in the general population and how this varies over time	Presence or absence of SARS-CoV-2 virus assayed from a nose and throat swab	Every calendar day from the start of the study, with analysis based on continuous time and the latest test available in the prior 2 weeks
Secondary Objectives		
To estimate the incidence of new symptomatic and asymptomatic SARS-CoV-2 infection in the general population, and how this varies over time	Presence of SARS-CoV-2 virus in a nose and throat swab, separately in previously negative and previously positive individuals (to estimate re-infection after clearing the virus)	Every calendar day from the start of the study
To estimate immunity to SARS-CoV-2 in the general adult population and how this varies over time, as reflected by anti-S and anti- N immunoglobins (anti-N in all participants to protocol v15.0 only)	Optical density readings for anti-S(spike) and anti-N(nucleocapsid) IgG from a ELISA assay for SARS-CoV-2 antibodies assayed from blood, categorised according to predefined thresholds based on pre-pandemic plasma as positive or negative	Every calendar day from the start of the study, with analysis based on continuous time and the latest test available in the last month
To estimate the association between prevalence of symptomatic and asymptomatic infection in individual members of households	Presence or absence of SARS-CoV-2 virus assayed from nose and throat swabs taken from different members of the same household*	Each household visit
To estimate the association between immunity to SARS-CoV-2 across individual members of households	Concentrations and thresholds of IgG to SARS-CoV-2 assayed from blood of different members of the same households*	Each household visit

Objectives	Outcome Measures	Timepoint(s) of evaluation of this outcome measure

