Up to protocol v15.0, participants who consent to one cross-sectional survey would have just one visit. Participants who consent to serial sampling would have either five study visits over one month (enrolment, weeks 1, 2, 3, 4) or at least 6 study visits over one year (enrolment; weeks 1, 2, 3, 4; then every month subsequently). The precise duration of follow-up would depend on when the participant was recruited and what they consented to – however, participants who agreed to monthly visits can withdraw permanently at any time and can also miss individual visits. From protocol v9.0 to protocol v15.0, the majority of participants agreeing to multiple follow-up visits after one month would have monthly visits through to April 2022. However, if some participants recruited before protocol v9.0 choose not to provide optional consent for follow-up through to April 2022, they would be followed for a maximum of 12 months (as the original consent form specified participation for a maximum of 12 months). Participants newly recruited under protocol v9.0 to v15.0 would be followed up monthly until April 2022, which would be between 3 and 9 months, depending on specific date of recruitment. From protocol v16.0, all participants will be followed up until the end of the study.

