16.8. Expenses and Benefits

Up to 1 April 2022, a small compensation (£50 voucher) will be offered to each consenting/assenting participant (including child participants) for each completed enrolment home visit (contact or noncontact) to reflect their time and inconvenience. For each subsequent completed serial sampling home visit, each participant will be offered a £25 voucher. This includes any additional visits after 12 months for those invited to extend follow-up for additional monthly visits through to April 2022. Vouchers can be posted to participants, but we will offer them the option of receiving the vouchers more quickly by email if they are happy to provide an email address for this purpose (email can also be used to receive test results and study updates). The total compensation per participant would therefore be £50 for a single visit, £150 for five visits over one month and £425 for 16 visits over one year; those consenting to additional monthly visits up to April 2022 would receive £425 plus or £25 for each extra visit up to April 2022 (total depending on date of original household enrolment).

Children and young people aged 5-15 years who attempt a blood draw for finger prick testing will receive a sticker as a "thank you" in the initial phase. Feedback from children and their parents in the initial phase indicated that this was not helpful or necessarily wanted and therefore stickers will not be given in the main phase of antibody testing in children and young people aged 8-15 years (those aged 5-7 years no longer included from protocol v13.0).

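### The ever- versus never-positive risk-factor analysis names no term for number of tests or calendar time at risk, so it is biased for any predictor linked to either

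*Protocol*

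**What the plan says.** Section 11.2 sets out the risk-factor analysis in three steps. First: "Associations between various predictors and ever testing positive for infection vs never testing positive will be estimated using unweighted proportions". These proportions are accompanied by "Fisher's exact tests with multivariable logistic regression models to adjust for confounding". On covariates: "Factors considered will include sex, ethnicity, age at last birthday (as both categorical and continuous variables) and other responses to the short questionnaire". A further sentence then adds: "These factors will also be considered in multi-level regression models, similar to the main model over continuous time described above".

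Number of swabs, length of follow-up and enrolment date do not appear among the named factors, and no offset or per-test denominator is given for the ever/never comparison. Section 11.4 includes everyone enrolled, with no minimum follow-up. Section 11.1 says that there is no formal statistical analysis plan.

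On exposure, the Synopsis allows one visit only, five visits, or at least six. Section 7 says "Participants who consent to serial sampling would have either five study visits over one month" or monthly visits beyond that. Section 16.8 gives the voucher total in pounds for a full year as "425 for 16 visits over one year". Section 7 also says that those recruited under protocol versions 9.0 to 15.0 would be followed for between 3 and 9 months, depending on recruitment date.

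**The concern.** Whether a person has ever tested positive depends on how often and in which months that person was tested, as well as on risk of infection. If a predictor is associated with testing exposure, the ever/never comparison mixes the two. The named covariates do not separate them, because none measures exposure. Fisher's exact test cannot take exposure into account at all.

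The protocol creates some of these links itself:

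- Section 9.4.4: when numbers were cut from April 2022, priority for retention went to non-White ethnicity, higher deprivation and smaller households, and to those with the longest participation and fewest missed visits.
- Section 7: later invitations to the blood cohort were increased for households with anyone from an ethnic group other than White. Section 9.4.1 ties that invitation to extended follow-up to April 2022.
- Section 7: follow-up length and calendar period both depend on enrolment date.

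Ethnicity is a named predictor. With samples of this size, a modest imbalance in exposure can appear as a highly significant risk factor, or can hide a real one.

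**Working it through.** **The plan's own visit count.** Week 0, weeks 1 to 4 and months 2 to 12 give 1 + 4 + 11 = 16 visits. Vouchers are 50 + 15 × 25 = 425 pounds for 16 visits and 50 + 4 × 25 = 150 pounds for five. Both match Section 16.8. A participant enrolled in April 2020 and followed monthly to March 2023 could reach about 1 + 4 + 34 = 39. A recruit with three months of follow-up has 1 + 4 + 2 = 7.

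**Inputs.** Per-test positivity p is 0.05% and 1.41% (the two August weeks in Section 9.4.3) and 3% (Section 11.3 speaks of rates above this). The significance level is 5% (Section 11.7), taken as two-sided. Assumptions: no true effect, constant p and independent tests.

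**Formula.** For k tests, P(ever positive) = 1 − (1 − p)^k, so the odds are (1 − p)^(−k) − 1.

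| p | Ever positive, k = 10 | k = 12 | k = 16 | OR 12 v 10 | OR 16 v 12 |
|---|---|---|---|---|---|
| 0.05% | 0.50% | 0.60% | 0.80% | 1.20 | 1.33 |
| 1.41% | 13.2% | 15.7% | 20.3% | 1.22 | 1.37 |
| 3% | 26.3% | 30.6% | 38.6% | 1.24 | 1.42 |

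At p = 1.41%, the odds after 16 and 12 tests are 0.2551 and 0.1858, and 0.2551 / 0.1858 = 1.37.

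**Chance of a false finding, 12 v 10 tests.** With 20,000 per group (an assumption), the null is rejected with probability 27% at p = 0.05%, 99% at p = 0.5%, and essentially 100% at p = 1.41% or 3%. With 5,000 per group and p = 1.41% it is 93%.

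**Choice of visit schedule alone.** Suppose 97% of one group and 93% of another take 16 tests and the rest take one. The odds ratio is then only 1.04 to 1.06 across p from 0.05% to 3%, with false rejection between 5% and 84% at 20,000 per group.

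**Calendar time can reverse the direction.** As a deliberately extreme case, 16 tests all at 0.05% give 1 − 0.9995^16 = 0.8% ever positive, while 7 tests all at 3% give 1 − 0.97^7 = 19.2%. The group with fewer tests looks far more infected.

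**Does an exposure term repair it?** Under the same assumptions, log(−log(1 − P)) = log k + log(−log(1 − p)), so a complementary log-log model with offset log k is exact. In 200 simulated datasets (p = 1.41%, 20,000 per group, mean 12 v 10 tests, no true effect), the ever/never logistic model gave a mean odds ratio of 1.22 and rejected in 100% of runs. With the offset the ratio was 1.00 and rejection was 5.0%, the nominal level. The offset handles number of tests only; calendar time needs its own term.

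**The case against.** The best defence is the next sentence of Section 11.2, which puts the same factors into multi-level models over continuous time. Those models estimate positivity at a given date, not whether a person was ever positive, so number of swabs does not drive them in the same way. This stands. A reader might infer that all of the plan's risk-factor work is biased; the document does not support that.

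Other stronger readings also go too far:

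- **Household clustering is ignored.** Section 11.4 says that analyses will adjust for it wherever possible and adds an analysis with one person per household. Fisher's test cannot do this, but the regression can.
- **Vaccination is forced into a fixed comparison.** The exploratory objectives in Section 6 specify vaccination status and time from vaccination.
- **The incidence method cannot deliver the split by prior status.** Section 6 wants incidence "separately in previously negative and previously positive individuals (to estimate re-infection after clearing the virus"), and Section 11.2 says "Incidence will be calculated indirectly by deconvoluting the Bayesian dynamic multi-level regression model estimate of swab positivity". It refers to a linked methods page for detail, which is not available here. The text does not say that only undivided positivity is used, so the failure is not established and is no part of this point.
- **Odds ratios near 3.5.** That is 16 tests against 5 for whole groups. Section 7 says that over 95% chose long follow-up, so the short schedules contribute little.
- **Every linked factor will show a false association.** The bias is in proportion to the link, and it may mask an effect.

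It is also fair to say that the covariate list is open-ended, so exposure adjustment is not forbidden. Section 9.4.4 states whom to retain, not observed retention, and its priority list does not include age. Section 9.4.2 later offered the extension to swab-only participants too, which weakens the link through the blood invitation. No document reports mean test counts by any predictor.

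**Conclusion.** The concern holds for the ever/never comparison only. Followed as written, it is biased in either direction for any predictor associated with number of tests or enrolment date. This is more than an omitted detail, because the chosen outcome and the Fisher test build the problem in.

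The size is illustrative: an odds ratio of about 1.2 for 12 v 10 tests and 1.37 for 16 v 12 at 1.41% per test, with no true effect. Both imbalances are assumed. Positivity also persists across weekly swabs and varies over time, so independence and constant positivity are simplifications. They affect the size of the bias, not its existence, and varying positivity can change its sign.

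Severity is moderate. Variation by participant characteristics is an exploratory objective, and the primary prevalence estimates do not use this model.

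**What to change.** Amend Section 11.2 so that the per-test, calendar-time multi-level models are the stated basis for risk-factor inference. They should use time-updated covariates such as vaccination and allow for clustering by participant and household.

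Then do one of the following with the ever/never Fisher and logistic comparison:

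1. drop it;
2. label it descriptive only, with no tests or causal wording; or
3. keep it with number of tests (for example a log offset in a complementary log-log model) and calendar time at risk included.

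Reporting the distribution of test counts and enrolment dates by each main predictor would let readers judge the remaining imbalance.

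The cost is protocol wording and a larger, slower model than a two-by-two table. The swab results and dates are already held, so no new data collection is needed.
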